2.7. Recruitment procedures

The recruitment strategy involves different stages (see figure 2), which include both the general practitioners' and the participants' recruitment. These stages are outlined below:

2.7.1. Recruitment and involvement of general practices into the study

This stage involves the recruitment of general practitioners. It is important to recruit enough general practitioners in order to have an adequate number of participants to the study (section 2.5). Insufficient recruitment can result in a limitation in power and generalizability of the study⁵⁰. In order to obtain enough general practitioners involved in the study, efforts were done to comply with the Solberg's seven R-factors⁵⁰. These factors include the relationship between recruiters and general practitioners, the reputation of recruiters, the requirements for study participation, the reward for participating to the study, reciprocity between what is provided by recruiters and what is expected by participants, resolute behavior of recruiters and respect between recruiters and participants⁵⁰. Several sub-stages are included within the stage of recruitment of general practitioners:

1. Getting in touch with the general practitioners in order to ask them their availability to join the research (large clinics of general practitioners are preferred). The first contact was brief but informative. General practitioners were contacted by:
 - In-person presentations at general practitioners' professional meetings
 - Cold calls to practices identified using local telephone books
 - Exploiting previous relationships between our general practitioners and their colleagues
 - Distributing flyers with the description of the study to general practitioners

2. Introductory meetings with general practitioners, the secretaries and nurses to confer the importance, contents and goals of the study.

Goals to be achieved with these meeting:

- General practitioners and their staff's understanding of the importance of the study.
- General practitioners and their staff's understanding of the recruitment methods.
- General practitioners and their staff's trust in the study and confidence in communicating research to their patients.
- General practitioners and their staff will have to feel morally rewarded by taking part in this research.

3. Meeting for the implementation of the recruitment strategy with general practitioners and their staff

- General practitioners were asked to help us advertising the study to other general practitioners.
- General practitioners were involved in the design of tailored recruitment procedures (i.e. in the initial brainstorming meetings and during the piloting stage of the recruitment) and as a source of feedback in the process of recruitment.
- Definition of the specific workload for each member of the study (e.g. researchers, general practitioners and their staff).

4. Beginning of recruitment after implementation of the recruitment strategy
 - A collaboration agreement and a data handling agreement with general practitioners was signed in order to avoid potential breach of data confidentiality and privacy.
5. Regular follow-up meetings with the general practitioners and the recruitment staff will be held in order to monitor the recruitment rate
 - Feedback about recruitment achievements will regularly be provided to the general practitioners and their staff. The recruitment rates from every practice will be monitored and every month an e-mail will be sent to each general practitioner who takes part in the study to provide them with statistics of both the overall and individual recruitment rate. If the number of participants recruited is lower than the expected rate (which will vary depending on the practice size), practices will be contacted to discuss reasons for the low participant rate ⁵¹.

2.7.2. Participant recruitment

Simple and broad entry criteria (described above in section 2.2) will be applied, in order to get as many participants as possible. A combination of strategies (please see figure 3), which are described below, has been taken into consideration.

The primary participant recruitment strategy will be the recruitment occurred at general practices on the day of consultation for knee pain (called “warm recruitment” within this document).

1. Warm recruitment. This method involves the invitation to join the study directly when children and adolescents have a consultation for knee pain at the general practice. If they agree to participate to the study, they will be provided with the study material (i.e. prognostic tool to be completed). In case children decide not to participate, the reason for non-participation will be asked from a list of options.

Alternative recruitment strategies that might be applied in order to maximize the recruitment rate

1. Advertisement of the study through social media (e.g. Facebook, Twitter, Snapchat).
2. Advertisement of the study through explicative posters that will be displayed at the participating general practices.

2.7.3. Strategies to increase baseline participation and limit loss to follow-up

In order to promote baseline participation and limit loss to follow-up from the study, children will be given two cinema tickets if they decide to take part in the study. The first ticket will be given at baseline, when children decide to take part in the study and after returning the questionnaire, and the second ticket will be given only if the children will have completed the follow-up (e.g. provided

information at both the 3-month and 6-month follow-up points). The ethics committee was informed about the cinema tickets to be given to participants and approved this method.

Figure 2

[figure not shown]
[figure not shown]

Figure 3

2.8. Data collection methods

2.8.1. Tool delivery at baseline

Data will be collected at baseline by means of a questionnaire (either with a paper-based questionnaire or collected with the support of a tablet) directly at the general practice when children and adolescents consult for knee pain. Alternatively, the questionnaire will be delivered at home or through a survey delivered with an internet link after that the children or their parents agreed to take part to the study if an alternative recruitment strategy will be applied (e.g. social media recruitment). In this case, children and their parents will be given the opportunity to choose between providing data through a paper-based questionnaire or a questionnaire delivered with an internet link.

2.8.2. Collection of data during follow-up

Data will be collected during follow-up from the children or parents through a questionnaire email-based or to be completed by text messages depending on the participants' preference. The questionnaire will include questions about pain characteristics (e.g. severity of pain, period free of knee pain, disability and activity limitations due to pain ^{42,48}) and about who is the person replying to the questionnaire (child alone/parent alone/child together with the parent). These questions will be taken from previously validated pain questionnaires or pain scales. Data collected at 3-month follow-up will be used to assess the primary outcome of the study, and data collected at 6-month follow-up will be used to assess the secondary outcome. In order to limit loss to follow-up, an e-mail/text message reminder will be sent to participants if they do not complete the follow-up questionnaire within one week from the day when they are supposed to reply. A second reminder

will be sent one week after the first reminder if they still will not have completed the follow-up questionnaire.

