1.5. Study design

Prospective cohort study. Data will be collected at baseline through a questionnaire delivered at the general practice if the primary recruitment strategy will be applied. Otherwise, the baseline collection of the data will occur through a questionnaire home-mailed or delivered through a survey internet link if a strategy of recruitment through social media will be applied (please see section 2.7.2 for a description of the recruitment strategies). Outcomes will be collected by questionnaires either self-reported or parent-reported (collected through e-mail or text messages) at follow-up.

2. Methods

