2.2. Participants and eligibility criteria

Children and adolescents who consult their general practitioner because of their knee pain (of both traumatic and non-traumatic origin) during a period of recruitment of 6 months (starting in July 2019) are eligible for inclusion.

2.2.1. Inclusion criteria:

- Age between 8 and 19 years old. The age of 8 is considered to be the lowest age for the children to be able to complete a pain questionnaire or a pain chart without adult guidance³⁸ (provided that the questions are properly worded by taking into account the age-related cognitive abilities^{39,40}), and the age of 19 is defined as the upper limit for the period of adolescence by the World Health Organization⁴¹.

2.2.2. Exclusion criteria:

- Age below 8 years old or over 19 years old
- Consultation for musculoskeletal pain only in a body region different from the knee

- Pain originated by different conditions (e.g. cancer, infections)
- Child is vulnerable (e.g. he/she has experienced a recent trauma and the distress may have an impact on the self-report making it not valid)³⁹
- Inability to take part to the study because of inability to understand or comply

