2.3. Outcome measures

The primary outcome measure will be the recurrence/persistence of activity-limiting knee pain (i.e. yes/no pain that is limiting activities in the same knee) at 3-month follow-up⁴². Participants will also be asked about continuity of their knee pain (i.e. “how long have you been free of knee pain?”), to enable the distinction between recurrence (on/off knee pain episodes between baseline and follow-up) and persistence (continuous knee pain from baseline to follow-up) of knee pain. A secondary outcome measure that will be collected is the recurrence/persistence of activity-limiting knee pain at 6-month follow-up.

Previous studies have shown an effect of the treatment received on the change in risk group for the recurrence/persistence of pediatric pain⁴³ and on the change in pain and function⁴⁴. Therefore, an additional outcome measure that might potentially be assessed include the treatment effectiveness on the recurrence/persistence of knee pain (provided that there will be the possibility to collect data on the treatment given). For practical reasons, it might be considered assessing this additional outcome on a subsample of children and adolescents.

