2.8.4. Pain assessment

Parents are involved in both the decision of seeking healthcare for musculoskeletal pain and in the discussion with the general practitioner during the clinical encounter ⁵². Therefore, it may occur that data reporting will actually be parent-report rather than child self-report, and this might introduce bias about the pain measurement, especially in longitudinal studies (i.e. children are too young to reliably self-report at the initial assessments, but they might self-report at later follow-up points) ⁵². Current evidence on pain reporting suggest that children are able to self-report from the age of 8 ³⁸, and that the agreement between child and parental report for the presence of pain

is around 50-70%, although the concordance is higher if the pain is of greater intensity and of longer duration ⁵². In addition, when their child's pain is severe, parents might over-report the severity of the impacts of pain on their children as they become more concerned about potential consequences of pain ⁵². Potential inaccuracies in the measurement of knee pain will be considered by means of a question about the persons responding to the follow-up questionnaire (e.g. child alone/parent alone/child together with the parent) as reported in section 2.7.2. Efforts will be done to encourage the same person to respond to all the follow-up questionnaires in order to reduce inaccuracies in pain reporting. For example, a strategy that might be adopted is to provide children with cinema tickets only if they will be the person responding to all the questionnaires.

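### The 3-month primary outcome may be answered by the child, a parent or both, and no planned analysis uses the record of who answered

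*Combined protocol and SAP*

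**What the plan says.** Section 2.3 defines the primary outcome as "yes/no pain that is limiting activities in the same knee) at 3-month follow-up", without naming a reporter. Section 1.5 leaves the reporter open: "Outcomes will be collected by questionnaires either self-reported or parent-reported". Section 2.8.2 does the same ("Data will be collected during follow-up from the children or parents") and then links this reply to the primary endpoint: "Data collected at 3-month follow-up will be used to assess the primary outcome of the study".

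The plan also treats self-report as feasible in the whole eligible age range. Section 2.2.1 gives age 8 as the "lowest age for the children to be able to complete a pain questionnaire or a pain chart without adult guidance", provided the questions are suitably worded, and section 2.8.4 repeats that children can self-report from that age.

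Section 2.8.4 recognises the difficulty: "it may occur that data reporting will actually be parent-report rather than child self-report, and this might introduce bias about the pain measurement". It says that agreement between child and parent on whether pain is present "is around 50-70%, although the concordance is higher if the pain is of greater intensity and of longer duration", and that parents may overstate the impact of severe pain. It offers three measures:
- A respondent question with three options (child alone, parent alone, both together): "Potential inaccuracies in the measurement of knee pain will be considered by means of a question about the persons responding to the follow-up questionnaire".
- Encouragement for the same person to answer all follow-up questionnaires.
- As a possibility only, cinema tickets that depend on the child being the one who responds.

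**The concern.** The outcome is a mixture of self-report and parent report, and the plan's own agreement figure says the two often differ. A child's case status can therefore depend on who filled in the form. The step 3 odds ratios, the AUC in step 4, the cut-offs in step 5 and the sensitivity, specificity and likelihood ratios in step 6 all rest on that status. Sensitivity and specificity are also the stated measures of predictive ability in section 1.4.

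The measures in 2.8.4 do not close the gap. The primary outcome uses one reply per child, so keeping the same respondent at 3 and 6 months does not make replies comparable between children. The ticket condition is optional, and section 2.7.3 gives the second ticket for completing follow-up whoever replies. The respondent question would help only if an analysis used it, and none is named.

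**Working it through.** **Is the respondent variable used anywhere?**
- Section 2.10, steps 1-6: descriptive analysis, floor and ceiling effects, regression, AUC, cut-offs and accuracy. Respondent is not mentioned.
- Section 2.10, step 7: stratifies by age group and sex only.
- Section 2.10, step 8: stratifies or adjusts by treatment received.
- Section 2.5: a sensitivity analysis on recruitment source.
- Section 2.11: a sensitivity analysis of complete cases against imputed data.

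Section 2.8.4 says the inaccuracy will be considered through the question, but gives no method.

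**The plan's own sample size.** Section 2.5: 168 practices x 5,000 x 0.20 aged 8-19 x 119/10,000 x 0.5 year x 0.30 participation = 299.9. This reproduces the stated 300 at baseline.

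**What 50-70% agreement means.** Between 30% and 50% of pairs are discordant. If child and parent each say yes half the time, chance agreement is 0.5² + 0.5² = 0.5. Kappa is then (0.5 - 0.5)/0.5 = 0 at the lower figure and (0.7 - 0.5)/0.5 = 0.4 at the upper.

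**Effect on the AUC.** Assumptions, because the documents do not give these figures:
- AUC of 0.75 against child report.
- 50% events at 3 months. The nearest figure in the plan is about 50% still in pain after 1 or 2 years (section 1.1).
- Disagreement symmetric and unrelated to the score.
- All 300 children answer.

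Let f = parent-alone share x (1 - agreement). At 50% events, observed AUC = 0.5 + (0.75 - 0.5) x (1 - 2f). The Hanley-McNeil standard error of an AUC of 0.75 with 150 events and 150 non-events is 0.028.

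| Parent-alone share | Agreement | f | Children classified differently, of 300 | Observed AUC | Loss / 0.028 |
|---|---|---|---|---|---|
| 10% | 70% | 0.03 | 9 | 0.735 | 0.5 |
| 20% | 70% | 0.06 | 18 | 0.72 | 1.1 |
| 30% | 60% | 0.12 | 36 | 0.69 | 2.1 |
| 50% | 50% | 0.25 | 75 | 0.625 | 4.5 |

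If agreement for this outcome were 80%, above the cited range, a 30% parent-alone share gives f = 0.06 and an AUC of 0.72.

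**The case against.** The strongest case on the other side has four parts.

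1. **The plan is not silent.** It foresees the problem, records the respondent, encourages consistency and floats child-only tickets. A reader might infer that recording the respondent is the only remedy; section 2.8.4 shows otherwise. What stands is narrower: these measures are not tied to any analysis, and they address consistency over time, not comparability between children.

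2. **The 50-70% may not transfer.** It concerns the presence of pain, not activity-limiting pain in a known painful knee, and the plan says agreement is higher for more intense or longer pain. This is fair. Real discordance may be smaller, so the lower rows of the table should not be read as expected values. The parent-alone share may also be low among those aged 15 or more, who give their own consent under section 2.13, though that is an inference.

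3. **Stronger readings do not hold.** A reader might infer that a child becomes a case if either reporter says yes. There is no such rule: one questionnaire is answered by the child, a parent or both together. A reader might also infer that parental over-reporting would create a false effect of younger age. The documents give neither the respondent split by age nor parents' rates of reporting pain. They describe over-reporting of impact when pain is already severe, and such children would mostly be cases anyway.

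4. **With one form per time point, a parent-alone reply is already one the child did not give.** Naming the child as primary reporter in the analysis alone would therefore change little. This stands, and it is why the question must be addressed to the child at collection, with the parent as a fallback.

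The printed baseline tool (section 2.6) has no respondent item either, so a change of reporter from baseline cannot be seen. That is secondary, because the outcome is follow-up status and not a change score.

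**Conclusion.** The concern holds in a limited form. The plan pools self-reported and parent-reported answers into one primary endpoint, cites evidence that they often differ, collects the variable needed to examine this, and assigns that variable to no analysis.

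The size cannot be fixed from the documents. Under the stated assumptions the loss of AUC runs from 0.015, about half a standard error and of little consequence, to 0.125. It exceeds two standard errors only when parent-alone replies are common and agreement is 60% or less. The direction is also not assured. Attenuation follows from error unrelated to the score. Error that varies with severity or age could bias accuracy either way, because severity may be related to the score.

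This is a change worth making, not a fatal flaw, and confidence in its practical size is medium.

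**What to change.** - **Sections 2.3 and 2.8.2:** address the follow-up question to the child. Define the primary outcome as the child's answer, given alone or with a parent. Accept a parent-alone answer only if the child has not replied after the planned reminders.
- **Section 2.10:** report the number of parent-alone outcomes, and repeat steps 3-6 excluding them. If they are few, they may instead be set to missing and imputed under 2.11. That section regards multiple imputation as suited to a low percentage of missing data, so exclusion should be the default if they are many.
- **Baseline form (optional):** add the same three-option respondent tick-box, outside the score, to describe changes of reporter.
- **Section 2.8.4:** correct the cross-reference for the respondent question, which points to 2.7.2; the question is in 2.8.2.

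The cost is a few sentences, one optional tick-box and one repeat analysis. The repeat analysis has somewhat fewer observed outcomes and so wider intervals. Fixing this in advance also prevents the reporter from being chosen after the results are known.

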2.8.3. Information about non-participation to the study and loss to follow-up

Information about reasons for baseline non-participation to the study (e.g. participant is too busy or not interested in the topic, or the participant has been considered not suitable to take part in the study by the general practitioner, or the general practitioner is too busy) will be collected by the person in charge of inviting the children to join the study. Information about reasons for baseline non-participation together with other data regarding non-participants (e.g. number, age, gender) will be used to describe the process of selection of participants ⁵¹.

Reasons for loss to follow-up will be assessed by contacting through a phone call/e-mail/text message those participants who do not reply to 3 consecutive follow-up reminders and asking about reasons for leaving the study.

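### The planned contact with children who stop replying asks only why they left; it could also ask the one-item outcome, once its timing is settled

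*Combined protocol and SAP*

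**What the plan says.** Section 2.3 defines the primary outcome as one binary item, "yes/no pain that is limiting activities in the same knee", at 3 months; the same item at 6 months is secondary. Section 2.8.2 takes it from an e-mail or text-message questionnaire: "Data collected at 3-month follow-up will be used to assess the primary outcome of the study".

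The same section plans two reminders. In the first, "an e-mail/text message reminder will be sent to participants if they do not complete the follow-up questionnaire within one week"; a second "will be sent one week after the first reminder if they still will not have completed the follow-up questionnaire". No third reminder is described.

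Section 2.8.3 then plans a further contact, the only follow-up step where a phone call is offered: "Reasons for loss to follow-up will be assessed by contacting through a phone call/e-mail/text message". It concerns "those participants who do not reply to 3 consecutive follow-up reminders and asking about reasons for leaving the study". Objective 4d in Section 1.4 likewise covers only the amount of loss and the reasons for it.

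The other measures on missing follow-up are a second cinema ticket that depends on completing both follow-ups (2.7.3), and imputation compared with a complete-case analysis (2.11).

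**The concern.** Staff who follow Section 2.8.3 as written will reach some children or parents, record why they stopped replying, and end the contact without the one answer that the analysis needs. That outcome stays unobserved and is later imputed or dropped.

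This could matter for two reasons. First, the target of 300 in Section 2.5 is a baseline number with no allowance for loss, so every missing outcome takes the analysed number below it. Second, children who have recovered may be less inclined to reply. If so, the observed proportion with activity-limiting pain is too high. Comparing imputed with complete-case results may not show this, because both draw on children who answered at some point. Section 2.11 itself notes that imputation is usually done when little is missing, so the fallback is weakest when loss is high.

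**Working it through.** **1. The plan's own figure.** Section 2.5: 168 practices × 5,000 persons × 20% aged 8–19 × 119/10,000 per year × 0.5 year × 30% participation = 299.88, against 300 stated. It reproduces, and it is a count at baseline.

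**2. When the contact would happen.** Section 2.8.2 gives reminders 1 and 2 weeks after the 3-month due date. Section 2.8.3 needs three unanswered in a row. If reminders are counted literally, the third is the first one for the 6-month questionnaire, about a week after that due date and roughly 3 months after the missed time point. A child who misses month 3 and replies at month 6 never triggers the contact. Only if the initial questionnaire counts as one of the three is the trigger met at the missed time point. The plan does not say which is meant.

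**3. Outcomes gained.** The documents give neither a loss rate nor a rate of answering at the contact, so both are assumed. With N = 300, loss d and fraction r of the lost answering, expected observed outcomes = 300 × [1 − d(1 − r)].

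| Loss d | r = 0 | r = 25% | r = 50% |
|---|---|---|---|
| 10% | 270 | 277.5 | 285 |
| 20% | 240 | 255 | 270 |
| 30% | 210 | 232.5 | 255 |
| 40% | 180 | 210 | 240 |

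These figures apply at 3 months only if the contact falls near the 3-month due date.

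**4. Worst-case bounds.** Assume 50% events among those observed; Section 1.1 gives about 50% persistence, but at 1 or 2 years, so this is a proxy. At 20% loss, 120 of 240 have the event. Counting all 60 missing as non-events, then as events, gives 120/300 = 40% to 180/300 = 60%. With half of the lost answering, 135 of 270 have it, and the bounds are 135/300 = 45% to 165/300 = 55%.

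**5. Bias in the event rate.** Assume a true rate of 50%, reply 85% if still in pain and 75% if recovered.
- Response: 0.5 × 0.85 + 0.5 × 0.75 = 0.80.
- Observed rate: 0.425/0.80 = 53.1%, a bias of 3.1 points.
- Half of the non-responders in each group answer: response becomes 0.5 × 0.925 + 0.5 × 0.875 = 0.90, and the observed rate 0.4625/0.90 = 51.4%, a bias of 1.4 points.

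**6. Accuracy measures under the same model.** Reply here depends on outcome alone. Sensitivity is the probability of a positive score given the event. Among responders with the event it is unchanged, because reply carries no further information on score. The same holds for specificity, likelihood ratios and AUC. Logistic odds ratios are also unchanged; the intercept moves by ln(0.85/0.75) = 0.125. So the event rate and predicted risks shift, and discrimination does not.

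**The case against.** The strongest objection is timing. On the literal trigger, the contact would seek a recollection about 3 months old, and using it as the 3-month outcome could replace missing data with misclassified data. This stands: adding the question without settling the trigger is not enough for the primary time point.

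Second, the illustrated gain is small: 53.1% to 51.4% is 1.7 points, against a 95% sampling margin of 1.96 × √(0.531 × 0.469/240) = 6.3 points. The example also lets both groups answer equally at the contact. If recovered children are again less inclined to answer, the bias falls by less. This stands too, although sampling error shrinks with more data and bias does not.

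Third, Section 2.8.4 cites child–parent agreement on the presence of pain of only about 50–70%, and a phone call may reach a parent. The respondent must therefore be recorded.

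A reader might infer three stronger claims that the documents do not support:
- **That the tool's accuracy is biased.** Step 6 shows that this needs non-response to depend on both score and outcome, and the documents contain nothing from which to size that.
- **That the reported prognosis is biased as a matter of fact.** Outcome-dependent non-response is plausible but not established.
- **That outcomes from this contact are the only evidence on the question.** Section 2.3 also asks how long the child has been free of knee pain. A child who misses month 3 and reports at month 6 more than 3 months without pain reveals the 3-month status. Section 2.11 does not restrict imputation to baseline predictors, so such answers could be used. They give nothing for a child who misses both follow-ups, and a shorter pain-free period does not show whether pain limited activity at month 3.

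The reminders and the ticket reduce loss, but obtain no outcome from a child who has nevertheless stopped replying.

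**Conclusion.** The point holds as an inexpensive improvement. The plan already intends to reach persistent non-responders, and by its stated content does not seek the outcome from those it reaches. That reading rests on the plan's silence: Section 2.8.3 states what is asked, and no other section adds to it.

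At an assumed 20% loss with 25% to 50% answering, the gain is 15 to 30 observed outcomes out of 300. Under the assumed reply rates and half answering, bias in the event rate drops by about 1.7 points. Actual yield is unknown, since some will not answer and Section 2.13 lets participants withdraw at any time. The further benefit is direct evidence on how non-responders fared. All of this depends on the contact following soon after the missed follow-up, which Sections 2.8.2 and 2.8.3 together do not secure.

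**What to change.** 1. Reconcile the two reminders in Section 2.8.2 with the three in Section 2.8.3, so that the contact follows soon after each missed follow-up.
2. For children who have not withdrawn, first ask the single activity-limiting knee pain item for that time point, then the reason for not replying.
3. Record date, mode and respondent (child, parent or both).
4. In Section 2.10 or 2.11, state in advance a window around the due date. Answers inside it count as the outcome in the main analysis; later, recalled answers enter a sensitivity analysis only. Repeat the main analysis without any answers obtained at this contact.

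The cost is one question in a contact already planned, a few database fields and two extra analyses. If the reconciled trigger brings the contact forward to each time point, there will be more contacts to make. The downside is that these answers come later, and sometimes by phone or from a parent; items 3 and 4 deal with that. The change has to be made before follow-up, because the answers cannot be collected reliably afterwards.
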